## 5.0 Analysis Populations

- Enrolled Population: All participants who sign informed consent.
- Randomized Population: All participants who are randomized, analyzed as per randomized treatment.
- Modified intent-to-treat (mITT) Population: All participants who are randomized and receive at least 1 dose of study medication, analyzed according to randomized treatment. All primary efficacy analyses will be conducted using this population.
- As Treated (Safety) Population: All participants who are randomized and receive at least 1 dose of study medication, analyzed according to treatment actually received. This population will be essentially the same as the mITT unless a participant received an incorrect treatment, i.e., a treatment different from what he/she was randomized to. All safety analyses will be conducted using this population.
- Pharmacokinetic (PK) Populations: All randomized participants who receive at least 1 dose of BMS-986036 and have any available concentration-time data. Available concentration-time data includes results that may be less than the lower limit of quantification (LLOQ). [REDACTED]

## 6.0 Statistical Methods

### 6.1 Efficacy Analyses

All efficacy analyses, both primary and secondary, will be performed on the Modified-Intent-to-Treat (mITT) population, unless otherwise specified, and analyzed according to randomized treatment..

#### 6.1.1 Primary Efficacy Analysis

The primary efficacy endpoint is the proportion of participants who achieve a  $\geq 1$ -stage improvement (as defined by NASH CRN Fibrosis Score) in fibrosis without worsening of NASH (as defined by NAFLD Activity Score) at Week 48, as determined by liver biopsy.

Improvement in fibrosis is defined as a decrease of fibrosis by  $\geq 1$  point, as determined by the NASH CRN Fibrosis Score. Worsening of NASH is defined as an increase of the NAFLD Activity Score (NAS) by  $\geq 1$  point.

Participants will be stratified at randomization by country (Non-Japan versus Japan). Participants in countries other than Japan will be stratified at randomization according to Type 2 Diabetes Mellitus (T2DM) status (yes versus no). Japanese participants will not be further stratified.

If lack of response in the strata prohibits analysis, the strata may be reduced to Japan/Non-Japan only or no stratification at all.

Sponsor: Bristol-Myers Squibb

Protocol No.: MB130-069

A Cochran-Armitage trend test of proportions at a one-sided 0.05 level of significance will be used to examine the linear trend among the proportions across treatment groups. The null hypothesis states that there is no association between treatment level and fibrosis stage improvement. The alternative hypothesis states that there is an association between treatment level and fibrosis stage improvement.

The proportion of participants with response will be summarized by strata as well as overall for each treatment group. Shift tables will be presented for the NAFLD Activity Score and NASH CRN Fibrosis Score. A bar chart of response/non-response in the primary endpoint will be provided.

All participants who prematurely discontinue from treatment without a biopsy at Week 48 (or ET, if applicable) or otherwise have a missing Week 48 (or ET, if applicable) biopsy result will be considered non-responders for the primary analysis of the primary efficacy endpoint.

All biopsy results will be included in the participant listings.

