9.3 Stratification

Randomization of participants will be stratified by country (Non-Japan/Japan). For participants in countries other than Japan, the randomization will be further stratified according to T2DM status (yes/no).

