9.5.2.1 Primary Endpoint

The primary endpoint is the proportion of participants who achieve a ≥ 1 -stage improvement in fibrosis (as defined by NASH CRN Fibrosis Score) without worsening of NASH (as defined by the NAFLD Activity Score) at Week 48, as determined by liver biopsy.

For this protocol, improvement in fibrosis is defined as a decrease of fibrosis by ≥ 1 point, as determined by the NASH CRN Fibrosis Score. Worsening of NASH is defined as an increase of the NAFLD Activity Score (NAS) by ≥ 1 point (see Section 8.5.1.1).

A Cochran-Armitage trend test with a one-sided 0.05 level of significance will be used to examine the linear trend among the proportions across treatment groups. Also, 95% confidence intervals for the odds-ratio of each BMS treatment group to placebo will be provided.

A sensitivity analysis using an extended Cochran Mantel-Haenszel (CMH) correlation test³⁷ will be used to assess the trend among the proportions for treatment groups with an adjustment to strata. A two-sided 0.10 level of significance will be used.

Since this is a Phase 2 study, no adjustment for multiplicity will be applied.

All participants who prematurely discontinue from treatment without a biopsy at Week 48 (or ET, if applicable) or otherwise have a missing Week 48 (or ET, if applicable) biopsy result will be considered nonresponders for the primary analysis of the primary efficacy endpoint. In addition, a completer analysis of the primary endpoint will be performed excluding participants without a Week 48 biopsy.

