## 2.3 Randomization

Randomization will be conducted in the following manner:

Participants will be stratified at randomization by country (Non-Japan versus Japan). Participants in countries other than Japan will be stratified at randomization according to Type 2 Diabetes Mellitus (T2DM) status (yes versus no). Japanese participants will not be further stratified.

- Eligible participants will be randomized by the IRT using a prespecified schedule in a double-blind manner to 10 mg BMS-986036, 20 mg BMS-986036, 40 mg BMS-986036, or placebo arms in a 1:1:1:1 ratio based on the stratification factors specified in [Section 2.1](#).
- The IRT will provide study treatment kit numbers that contain the appropriate study treatment (BMS-986036 or placebo) for dispensation to that participant.

At subsequent study visits, the investigator or designee will access the IRT to receive the corresponding kit numbers assigned to the participant for the purpose of dispensing study treatment.

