#### 6.1.1.1 Sensitivity Analyses

There will be a sensitivity analysis of primary efficacy endpoint to determine the effect of the stratification variables Japan and T2DM. A Logistic regression model will be used with randomized stratification factors as main fixed effects and NASH score at baseline as well as treatment. We will have all pairwise dose comparisons against placebo and trend test with a one-sided test at alpha = 0.05 with point estimate and two-sided 90% CI will be provided. Odds ratio point estimate and two-sided 90% CI. Average across the dose groups and comparison to placebo using a nominal one-sided test at alpha=0.05 will be calculated.

A sensitivity analysis using an extended Cochran Mantel-Haenszel (CMH) correlation test will be used to assess the trend among the proportions for treatment groups with an adjustment to strata. A two-sided 0.10 level of significance will be used.

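### The trial randomises within three strata, but the primary trend test ignores them; making the already planned stratified test primary is a cheap, modest and conditional gain in efficiency

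*SAP*

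**What the plan says.** **Randomisation.** Protocol 8.1 and 9.3 and SAP 2.3 stratify by Japan against all other countries, and outside Japan also by T2DM status. Japanese participants are not split further, so there are three strata.

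**Primary test.** SAP 6.1.1: "A Cochran-Armitage trend test of proportions at a one-sided 0.05 level of significance will be used to examine the linear trend among the proportions". Protocol 9.5.2.1 names the same test at the same level. Neither mentions strata in the test. The power statement in protocol 9.1 also rests on the Cochran-Armitage test.

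**Where the strata are used.** Protocol 9.5.2.1 plans an extended CMH correlation test that "will be used to assess the trend among the proportions for treatment groups with an adjustment to strata", as a sensitivity analysis at two-sided 0.10. SAP 6.1.1.1 repeats it and adds a second one: "A Logistic regression model will be used with randomized stratification factors as main fixed effects". SAP 6.1.1 also tabulates response by stratum.

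**A sentence without a clear home.** SAP 6.1.1, just before it names the unstratified test, says: "If lack of response in the strata prohibits analysis, the strata may be reduced to Japan/Non-Japan only or no stratification at all".

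**Secondary endpoints.** SAP 6.1.2 applies the primary method to all six.

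**The concern.** A trial that balances its arms within strata has already paid for a more precise comparison. If the strata predict response, a pooled test leaves the between-stratum variation in its variance estimate although the design has removed it from the treatment contrast. The test statistic is then too small on average, the true one-sided level falls below 5%, and some power is lost.

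At stake is the ranking of two tests that will both be run. When the strata are prognostic and balanced, nearly all disagreements go one way: the sensitivity test is significant and the primary test is not. The same ranking passes to the secondary endpoints.

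**Working it through.** **1. Reproduce the stated power.** Inputs from protocol 9.1: response rates 15, 20, 30 and 40%, 25 per arm, one-sided 0.05. The documents give no trend scores; 0, 1, 2, 3 are assumed, so the deviations d are -1.5, -0.5, 0.5 and 1.5, with sum of squares 5.

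- Expected numerator: n × Σ(d × p) = 25 × (-0.225 - 0.100 + 0.150 + 0.600) = 25 × 0.425 = 10.625.
- Null variance: mean rate 0.2625, so 0.2625 × 0.7375 × 25 × 5 = 24.20 (SD 4.919).
- Variance under the alternative: n × Σ(d² × p(1-p)) = 25 × 0.9194 = 22.98 (SD 4.794).
- Power: Φ[(10.625 - 1.645 × 4.919) / 4.794] = Φ(0.528) = 70.1%.

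This agrees with the protocol's figure of at least 70%. Dose scores 0, 10, 20, 40 give 69.6%. At 38 per arm with scores 0 to 3: Φ[(16.15 - 1.645 × 6.065) / 5.911] = Φ(1.045) = 85.2%.

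**2. Compare the two tests on the same data.** Both use scores 0 to 3 and one-sided 0.05, which is the upper half of the planned two-sided 0.10 CMH test.

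- Pooled: z = Σ x(s - s̄) / √[r(N-r)/N² × SS], with x the responders per arm, r the total responders and SS the sum of squares of the scores.
- Stratified: z = Σ over strata of the same numerator / √[Σ over strata of r(N-r)/(N(N-1)) × SS].

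Assumptions, none of them in the documents: shares for Japan/T2DM/no T2DM of 10/65/25, 10/45/45, 20/60/20 and 5/75/20% (per arm 4/25/9, 4/17/17, 8/23/7 and 2/28/8); equal arms within each stratum; an odds ratio (OR) for response without T2DM against the other two strata. Overall arm rates are held at 15/20/30/40% with 38 per arm. There were 200,000 simulated trials per setting.

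| OR | Pooled / stratified power, 10/65/25 mix | Stratified minus pooled, all mixes (points) | Same, 20% of biopsies missing and counted as non-response |
|---|---|---|---|
| 1 | 85.8 / 85.5% | -0.2 | 0.0 |
| 2 | 86.0 / 86.1% | +0.1 to +0.2 | +0.4 to +0.5 |
| 3 | 86.3 / 87.0% | +0.6 to +0.8 | +1.0 to +1.2 |
| 4 | 86.7 / 87.9% | +1.1 to +1.3 | +1.7 to +1.9 |
| 8 | 87.8 / 90.6% | +2.6 to +2.9 | +3.7 to +4.5 |

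If Japan is the stratum that differs, with nothing missing, the difference is -0.1 to +0.1 (OR 2), +0.3 to +1.2 (OR 4) and +0.9 to +2.8 (OR 8).

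**3. Level.** At a common 15% rate, the pooled test's one-sided error is 5.1 to 5.3% at OR 1 and falls to 4.0 to 4.4% at OR 8. The stratified test stays at 4.9 to 5.1%.

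**4. Disagreements.** At OR 4, only the stratified test is significant in 1.1 to 1.3% of trials, and only the pooled test in 0.01%. At OR 1 the order reverses: pooled only 0.3%, stratified only under 0.1%.

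**5. Test the downside (10/65/25 mix).**

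- Lower response rates, assumed 5/8/12/16%: -1.0 (OR 1), -0.6 (OR 2), 0.0 (OR 3), +0.6 (OR 4).
- Protocol rates but simple randomisation within strata, an extreme case of chance imbalance: -0.5 to -0.6 (OR 1), about 0 (OR 2), +1.0 (OR 3).

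**6. The strata-reduction sentence.** The primary test has no strata to reduce. In the CMH test a stratum with no responders has r = 0 and adds zero to both numerator and variance, so that test does not need the rule.

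**The case against.** The strongest reply is that this is a choice between two valid, prespecified tests. The documents agree on which one is primary, the power statement matches it, and every stratified result will be reported anyway. This is a Phase 2 trial without multiplicity adjustment, and protocol 6.2.1 rests later design and dose selection on the totality of the evidence. The gain exceeds 1 point only at odds ratios of about 4 or more (about 3 if a fifth of biopsies are missing), and nothing in the documents supports effects of that size. If the strata are weak, the switch can lose power.

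Most of this stands, and it limits the point to a cheap improvement. The loss is not capped at 0.2 points: step 5 shows up to about 1 point, in a low-response setting that SAP 6.1.1 itself contemplates. What does not follow is that the ranking is immaterial, because with balanced prognostic strata the trial would miss its primary test in cases where its own planned sensitivity test succeeds.

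Two stronger readings are tempting. A reader might infer that ignoring the strata inflates false positives; step 3 shows that prognostic strata push the error the other way. A reader might also infer that the strata-reduction sentence lets the primary result be changed after the data are seen; it cannot, because that test uses no strata. Assigning the sentence to the logistic model is plausible, but it is inference: the SAP does not say which analysis it governs.

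**Conclusion.** The point holds as one of efficiency, not validity. The primary test, and through SAP 6.1.2 the secondary analyses, leave out strata that the randomisation already uses. The power statement needs no correction.

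At 38 per arm and the protocol's rates, stratifying changes power by -0.2 points if the strata are not prognostic and by +2.6 to +2.9 at an odds ratio of 8. With absent or weak effects, the loss is about 0.2 points in balanced strata, about 0.5 to 0.6 with chance imbalance, and up to about 1 point at much lower response rates. All these sizes depend on assumed stratum shares, effects and trend scores. The change is worth making because it is cheap, not because the present test is wrong. The strata-reduction sentence is a minor matter of wording.

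**What to change.** Before unblinding, amend protocol 9.5.2.1 and SAP 6.1.1 and 6.1.1.1:

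- Make the extended CMH correlation test, stratified by the three randomisation strata and one-sided 0.05 in the direction of improvement, the primary analysis. SAP 6.1.2 then carries it to the secondary endpoints.
- Keep the unstratified Cochran-Armitage test as the sensitivity analysis, and note that the 70% power was computed for it.
- State which analysis the strata-reduction sentence governs. If it is kept, give it a fixed trigger that can be checked on blinded data, such as a stratum with no responders over all arms combined.

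No new analysis is needed, since both tests are already planned, and SAP 1.0 allows tracked changes with final approval before database lock. The cost is an amendment of the primary-analysis text in both documents after enrolment has closed, a primary test that is no longer the one in the power statement, and the possible small loss of power given above.

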#### 6.1.1.1 Sensitivity Analyses

There will be a sensitivity analysis of primary efficacy endpoint to determine the effect of the stratification variables Japan and T2DM. A Logistic regression model will be used with randomized stratification factors as main fixed effects and NASH score at baseline as well as treatment. We will have all pairwise dose comparisons against placebo and trend test with a one-sided test at alpha = 0.05 with point estimate and two-sided 90% CI will be provided. Odds ratio point estimate and two-sided 90% CI. Average across the dose groups and comparison to placebo using a nominal one-sided test at alpha=0.05 will be calculated.

A sensitivity analysis using an extended Cochran Mantel-Haenszel (CMH) correlation test will be used to assess the trend among the proportions for treatment groups with an adjustment to strata. A two-sided 0.10 level of significance will be used.

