8.3.1 Inclusion Criteria

1. Signed written informed consent
 - a) Participants must be willing to participate in the study and sign the informed consent form(s) (ICF[s])
 - b) Participants (and caregivers as applicable) must be willing and able to complete all study-specific procedures and visits
2. Liver biopsy performed within 6 months (26 weeks) prior to the Screening Period. Biopsy performed prior to ICF must be available to the central reader prior to randomization. If historical biopsy is not available, a liver biopsy will be performed during the Screening Period (see Section [8.5.1.1](#)). Biopsy must be consistent with NASH and cirrhosis according to the NASH CRN classification, as assessed by the central reader.
3. Participants taking anti-diabetic, anti-obesity, or anti-dyslipidemic medications must have been on stable regimens for at least 3 months (12 weeks) (6 weeks for statins) prior to and during the Screening Period. The investigator may contact the medical monitor regarding the stability of a participant's regimen when determining eligibility for study participation. Participants taking vitamin E at doses ≥ 800 IU/day must have been on stable doses for at least 6 months (26 weeks) prior to and during the Screening Period. Vitamin E treatment (≥ 800 IU/day) must not have been initiated after the qualifying liver biopsy was performed.
4. Age and reproductive status
 - a) Men or women 18 to 75 (inclusive) years of age
 - b) Women of childbearing potential (WOCBP) must have a negative pregnancy test (minimum sensitivity 25 IU/L or equivalent units of human chorionic gonadotropin) within 24 hours prior to the start of study medication
 - c) Women must not be breastfeeding at any time during the study

- d) WOCBPs must agree to follow instructions for method(s) of contraception for the duration of treatment (BMS-986036 or placebo) plus 5 half-lives of study medication (5 days) plus 30 days (duration of ovulatory cycle) for a total of 35 days after the end of the Double-Blind Treatment Period
- e) WOCBPs who are continuously not heterosexually active are exempt from contraceptive requirements but must undergo pregnancy testing as described in the Schedule of Activities in Section 1

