8.3.8.2 Rescreening

This study will permit the rescreening of a participant who has discontinued the study as a pre-treatment failure (i.e., the participant has not been randomized/has not been treated). Consultation with the medical monitor may be needed to identify whether rescreening is clinically relevant. If rescreened, the participant must sign a new ICF.

In the event that histologic evaluation of the biopsy of an otherwise qualified participant results in a diagnosis of NASH with stage 3 fibrosis, that individual is not eligible for the present study (MB130-069) but may be considered for enrollment under protocol MB130-068 (A Phase 2b Randomized, Double-Blind, Placebo-Controlled Study Evaluating

the Safety and Efficacy of BMS-986036 (PEG-FGF21) in Adults with Nonalcoholic Steatohepatitis [NASH] and Stage 3 Liver Fibrosis). Laboratory parameters and/or assessments that were collected as Screening procedures for this study (MB130-069; [Table 1](#) in Section 1) may be utilized for the same purpose for MB130-068.

Conversely, in the event that histologic evaluation of the biopsy of an otherwise qualified participant for MB130-068 results in a diagnosis of NASH with cirrhosis, that individual is not eligible for the MB130-068 study but can be considered for enrollment under the present study (MB130-069). Laboratory parameters and/or assessments that were collected as Screening procedures for MB130-068 may be utilized for the same purpose (Table 1 in Section 1) in this study (MB130-069).

For participants who are rescreened, consult with the medical monitor to confirm which parameters and/or assessments that were collected as part of the original Screening Period procedures may be utilized.

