#### Fibrosis

#### NASH CRN Fibrosis

Fibrosis is staged separately from NAS on a 0-4 scale: 0 (none); 1 (perisinusoidal or periportal fibrosis); 2 (perisinusoidal and portal/periportal fibrosis); 3 (bridging fibrosis); 4 (cirrhosis).

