#### Ishak

A modified Ishak scoring system will also be used to stage fibrosis in the histologic samples. The Ishak system (0-6 scale) was originally developed to grade portal-based liver fibrosis associated with viral

Sponsor: Bristol-Myers Squibb

Protocol No.: MB130-069

hepatitis. The modified Ishak system has been adapted to stage central-based liver fibrosis associated with NASH, and it also uses a 0-6 scale:

- 0: No fibrosis
- 1: centrilobular pericellular fibrosis
- 2: centrilobular and periportal fibrosis
- 3: bridging fibrosis (few bridges)
- 4: bridging fibrosis (many bridges)
- 5: early or incomplete cirrhosis
- 6: established or advanced cirrhosis

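### The sensitivity logistic model for the primary endpoint has no usable baseline fibrosis covariate, although the modified Ishak stage could supply one

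*SAP*

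**What the plan says.** **Entry.** Protocol 8.3.1, criterion 2: "Biopsy must be consistent with NASH and cirrhosis according to the NASH CRN classification, as assessed by the central reader". Cirrhosis is stage 4, the top of the CRN fibrosis scale (SAP 8.6). For a biopsy read as stage 3, Protocol 8.3.8.2 says "that individual is not eligible for the present study (MB130-069) but may be considered for enrollment under protocol MB130-068".

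**Primary analysis.** SAP 6.1.1 uses an unadjusted Cochran-Armitage trend test at one-sided 0.05.

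**Sensitivity analyses.** SAP 6.1.1.1 has two. The first: "A Logistic regression model will be used with randomized stratification factors as main fixed effects and NASH score at baseline as well as treatment". It supplies a trend test, each dose against placebo with odds ratios and 90% intervals, and the dose average against placebo. The second is an extended CMH correlation test, which "will be used to assess the trend among the proportions for treatment groups with an adjustment to strata". The strata are Japan/non-Japan and, outside Japan, diabetes status.

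**Ishak.** SAP 8.6: "A modified Ishak scoring system will also be used to stage fibrosis in the histologic samples". Its stages include "5: early or incomplete cirrhosis" and, above that, stage 6 for established or advanced disease. Baseline Ishak is needed for the secondary endpoint of at least one stage of Ishak improvement (SAP 4.2) and for the exploratory improvement categories and shifts (SAP 4.5, 6.4). Nowhere is it a covariate or a stratum.

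**The concern.** A responder must move from CRN stage 4 to stage 3 or lower. Everyone starts at the same CRN stage, so that scale cannot say who is near the boundary and who is far from it. The Ishak labels suggest that a biopsy read as early or incomplete cirrhosis lies nearer to it. If so, baseline Ishak predicts response, and a chance difference in Ishak mix between arms carries into the estimates.

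Within the SAP, the logistic model is the only source of dose-versus-placebo odds ratios and of the averaged-dose comparison for the primary endpoint. Protocol 9.5.2.1 also promises odds-ratio intervals but names no model. Phase 3 dose selection is to draw partly on this study's efficacy results (Protocol 6.2.1). The SAP's habit elsewhere is to adjust: SAP 6.4 adjusts continuous endpoints such as CPA, MRE and Fibroscan for their own baseline. The binary fibrosis endpoint has no counterpart.

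**Working it through.** **1. The covariate in the model.** There are two readings of the undefined score.
- NAS: steatosis, inflammation and ballooning. No fibrosis content.
- CRN fibrosis stage: equal to 4 for everyone, eligibility deviations aside. A design matrix with intercept, dose and a column of 4s has rank 2 of 3, so the effect cannot be estimated.

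**2. The plan's own power figure.** Inputs from Protocol 9.1: rates 15/20/30/40%, 25 per arm, one-sided 0.05. With equally spaced scores centred at zero (-1.5, -0.5, 0.5, 1.5):
- mean of the statistic: 25 x (-1.5x0.15 - 0.5x0.20 + 0.5x0.30 + 1.5x0.40) = 10.63
- null variance: 0.2625 x 0.7375 x 25 x 5 = 24.20; alternative variance: 22.98
- z = (10.63 - 1.645 x 4.92)/4.79 = 0.53, so power is 70.1%

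This reproduces the stated 70%. At 38 per arm the same formula gives 85.2%.

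**3. Power with and without Ishak.** Neither the share at Ishak 5 nor the response odds ratio (OR) for 5 vs 6 is in the documents, so both are assumed. Trials were simulated with 38 per arm and marginal rates held at the planned values. The logistic trend model contained dose, with or without one binary Ishak term; strata, NAS and missing biopsies were left out.

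| OR | Share 30%: without / with | Share 50%: without / with |
|---|---|---|
| 1 | 85.7 / 85.7% | 85.9 / 85.8% |
| 2 | 85.0 / 85.9% | 85.8 / 86.5% |
| 3 | 86.1 / 87.7% | 86.5 / 87.2% |
| 4 | 85.1 / 87.9% | 85.6 / 88.1% |
| 5 | 85.0 / 88.6% | 86.5 / 89.2% |
| 8 | 85.3 / 91.1% | 85.7 / 90.0% |

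Rows OR 3 and 5 use a score test (3,000 trials each); the others use a Wald test (4,000 each). Each single figure has a simulation standard error of about 0.6 points. Both columns of a pair use the same trials.

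**4. Chance imbalance, one dose against placebo.** The SD of the difference in Ishak 5 share is sqrt(2w(1-w)/38): 10.5 points at w = 0.3 and 11.5 at w = 0.5. A gap of 15 points or more, in either direction, then has probability 15-19% by the normal approximation (17-21% in simulation).

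Such a gap shifts the response difference by 0.15 x (p5 - p6), where p5 and p6 are the response rates at Ishak 5 and 6. At the 15-20% rates of the 10 mg and placebo arms:
- smallest at OR 3-5 (share 50%, OR 3, rate 15%): 0.15 x (21.6 - 8.4) = 2.0 points
- largest at OR 3-5 (share 30%, OR 5, rate 20%): 0.15 x (39.6 - 11.6) = 4.2 points

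**5. Set against total sampling error.** The SE of the 10 mg-placebo difference is sqrt((0.15x0.85 + 0.20x0.80)/38) = 8.7 points. The part due to Ishak mix has variance w(1-w)(p5-p6)²/38 per arm, summed over both arms. That is about 4-9% of the total at OR 3-5 and under 2% at OR 2. Removing it takes the SE from 8.7 to 8.3-8.5 at OR 3-5.

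**The case against.** The strongest reply is that nothing here is an error. The decision rests on the unadjusted trend test, which randomization makes valid. The logistic model's declared purpose is to examine Japan and diabetes, and the choice of covariates in a sensitivity model is discretionary. That stands, and it limits the weight of the point.

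A reader might infer that an Ishak imbalance biases the primary result or inflates type I error. It does neither. A reader might also set a shift of 2-4 points beside the planned 5-point effect of 10 mg and conclude that imbalance could create or erase it. Chance imbalance is already inside the 8.7-point standard error and is a small part of it, and the trial was sized on the trend, not on that contrast.

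Three further objections hold in part.
- **Prognostic value is inferred.** It is read from the scale labels. The documents give no response rate by Ishak stage and no cross-tabulation with CRN stage. Protocol 8.5.1.1 concedes considerable variation in fibrosis staging, which would weaken the assumed odds ratio.
- **Responders are few.** Planned rates give 38 x (0.15 + 0.20 + 0.30 + 0.40) = 40, fewer with missing biopsies, which count as non-response. The model already carries about six terms (three doses, two for strata, one score), and SAP 6.1.1 foresees dropping strata for lack of response. This argues for one binary term, not against any term.
- **Imbalance would be partly visible.** Ishak shifts would show each arm's baseline mix. They would not adjust for it.

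Baseline CPA is a reasonable alternative covariate. Ishak has the advantage that its stages divide cirrhosis itself.

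**Conclusion.** The point holds as a modest improvement to a sensitivity model. As written, SAP 6.1.1.1 offers one disease covariate that is undefined and, on either reading, is not a usable fibrosis measure. A baseline fibrosis measure that varies within cirrhosis is needed anyway for a secondary endpoint and is left out of the model.

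The size depends wholly on assumptions. With 30-50% at Ishak 5 and 38 per arm, the gain in power of the model-based trend test is about 0-1 point at OR 1-2 and about 1-4 points at OR 3-5. It is larger only if Ishak is very strongly prognostic (4-6 points at OR 8). If Ishak is not prognostic the loss is negligible, at most 0.1 point in these simulations. The documents do not support saying that the primary conclusion is at risk, or that baseline Ishak serves only for shift tables: it also defines the Ishak improvement endpoints. Ambiguity over the NASH score needs correcting whatever is decided about Ishak.

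**What to change.** Before unblinding, replace the baseline NASH score in SAP 6.1.1.1 with: *baseline NAS and baseline modified Ishak stage (5 or lower vs 6, one binary term)*. Use that model for its trend test, each dose against placebo and the averaged-dose comparison. Leave the primary Cochran-Armitage test unchanged. State that, if response is too sparse to fit the model, the strata terms are dropped first; this extends the allowance already in SAP 6.1.1.

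The cost is one SAP sentence, recorded in the change log that SAP 1.0 provides for, with no new data. The downside is one more parameter: about seven terms instead of six on about 40 expected responders, or 40/7 = 5.7 responders per term against 40/6 = 6.7.
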